Our unique combination of pediatric and adult endocrinology skills, laboratory expertise in insulin signaling, and clinical research experience in insulin sensitivity testing in obese youth make us perfectly poised to address these hypotheses. In addition, the use of a longitudinal study design will allow us to examine differences in percent body fat, body fat distribution and changes in BMI over time in the observational arm of the study. It also allows to examine whether treatment of obese children during this time can have beneficial effects on insulin sensitivity and secretion in the treatment arm. Enhancing our understanding of longitudinal changes of insulin sensitivity in obese adolescents and the response to metformin will help us identify potential interventions aimed at the prevention of T2DM.

The studies in this proposal will test the following hypotheses:

HYPOTHESES:

- 1. Obese adolescents, unlike normal weight controls, fail to improve insulin sensitivity at the end of puberty.**
- 2. Treatment of obese adolescents with metformin during puberty will help these individuals result in sustained improvement in insulin sensitivity at the end of puberty, decrease compensatory hyperinsulinemia, and preserve insulin secretion, thereby improving their disposition index (DI).**

To test these hypotheses, we propose to address the following Specific Aims:

SPECIFIC AIM 1 (Observational Arm):

- 1. To compare longitudinal changes in insulin sensitivity and secretion and their correlates in obese and normal weight adolescents during puberty.**
 - a. To compare changes in insulin sensitivity and secretion as measured by frequently sampled intravenous glucose tolerance test (IVGTT) from early puberty to puberty completion between obese and normal weight adolescents.**

- b. To compare changes in body composition, fat distribution, and inflammatory markers over time between these groups.**

Under this Specific Aim, insulin sensitivity and secretion will be measured by frequently sampled IVGTT in early puberty and at puberty completion in obese and normal weight adolescents. Changes in insulin sensitivity will be correlated with changes in inflammatory markers in all participants and body composition in a subset of these participants.

[figure not shown]
SPECIFIC AIM 2 (Treatment Arm):

- 2. To compare changes in insulin sensitivity and secretion and their correlates, in obese adolescents treated with metformin or placebo during puberty.**

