 - a. To compare changes in insulin sensitivity and secretion from early puberty to puberty completion between obese controls and obese adolescents treated with metformin.**
 - b. To compare changes in body composition, fat distribution, and inflammatory markers over time between these groups.**

Under this Specific Aim, obese participants from Specific Aim 1 will be randomized to receive placebo or metformin treatment during puberty. Frequently sampled IVGTT will be performed to measure insulin sensitivity and secretion in early puberty, at the end of puberty when treatment is stopped, as well as six months after treatment completion. Changes in body composition will also be measured in a subset of participants and changes in inflammatory markers will be measured in all participants at these time points.

The nested study design (Fig 1) will efficiently address four important knowledge deficits with a single recruited cohort: 1) Whether obese adolescents recover their pre-pubertal insulin sensitivity at the end of puberty; 2) The relationships between longitudinal changes in insulin sensitivity and changes in body composition in obese and normal weight youth; 3) Whether treatment with metformin during puberty can improve insulin sensitivity in obese adolescents to the level seen in normal weight pubertal adolescents; and 4) Whether treatment of obese adolescents during puberty will result in prolonged improvement of insulin sensitivity and secretion.

Fig. 1

B. BACKGROUND AND SIGNIFICANCE

Insulin Resistance and T2DM in Youth

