After determination of eligibility, participants will have a one-day CTRC admission for baseline laboratory studies, IVGTT, and body composition assessment (Study Visit 1) following an overnight fast. Upon arrival they will have an IV placed for blood draws and injections. Fasting blood glucose and insulin will be drawn at this time. Sex steroids and inflammatory markers will also be drawn at this time. (After the blood draw, they will undergo a frequently sampled IVGTT (specific methods for above described after Specific Aim 2). Up to 10 obese subjects will participate in the arm, as pilot subjects, who **are not** part of the treatment arm (i.e. they will not be taking a placebo).

In the afternoon of the Study Visit 1, a dual-energy x-ray absorptiometry (DEXA) scan will be performed to determine body composition. In a subset of participants (13 per group), soleus muscle nuclear magnetic resonance (NMR) and abdominal fast magnetic resonance imaging (MRI) sequence will also be performed to measure body fat distribution in terms of IMCL, liver fat content and visceral adipose content.

The next study visit (Study Visit 2) will occur when the participant has reached Tanner stage IV, approximately one year after the baseline visit. At this time the baseline laboratory draw, imaging studies and IVGTT will be repeated. For those subjects randomized to the MRI, it will not be repeated at this visit.

The next study visit (Study Visit 3) will occur when the participant has reached Tanner stage V, approximately one year after Study Visit 2. At this time the baseline laboratory draw, imaging studies and IVGTT will be repeated. This is the last long visit for the lean subjects. The obese subjects will stop taking the study medication at this time point.

The next study visit (Study Visit 4) will occur 6 months after the obese participants have reached Tanner stage V. At this time the baseline laboratory draw, imaging studies and IVGTT will be repeated. This is the last long visit for the obese subjects. For those subjects randomized to the MRI, it will not be repeated at this visit.

Between the visits, participants will be asked to come in every 6 months for anthropometric measurements and Tanner staging. Obese participants in the treatment arm (randomized to either Metformin or placebo) will also be asked to come in quarterly for pill counts to measure medication compliance and to receive a refill on their medication.

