In adolescence, the number of routine visits to the pediatrician tends to drop. Therefore, we foresee a potential difficulty in recruiting children who are just starting puberty. For this reason, we are including children who are both Tanner 2 and Tanner 3 at study entry. In both of these stages of puberty, insulin sensitivity has been shown to be significantly decreased when compared with Tanner 1 and Tanner 5. The length of time required for progression through puberty varies in individuals. It is important to measure the post-treatment insulin sensitivity in Tanner stage 5, because insulin sensitivity in Tanner 4 may not be significantly different from earlier in puberty and only at T5 insulin sensitivity returns to its pre-pubertal level. For this reason, if a subject has not reached Tanner 5 in two years, they will not have their Study Visit 3 until Tanner 5 has been attained. This means that some subjects may need to be treated for a longer period of time. However, in order to compare differences in insulin sensitivity after treatment is stopped between subjects, the interval from treatment stop (Study Visit 2) to post-treatment follow-up (Study Visit 3), should be consistent.

The natural recovery of pubertal insulin sensitivity may confound measurement of metformin effects on insulin sensitivity as puberty progresses. In order to control for this, we have included a placebo-controlled group and a group of normal weight controls. This will allow us to compare changes in insulin

sensitivity from baseline to the end of puberty between obese treated subjects and both normal-weight and obese subjects who have not been treated.

The length of this study and potential difficulty with attrition are also limitations of this study. To limit the number of participants lost to follow-up, we will maintain frequent contact with participants with quarterly visits for anthropometric measurements, monthly visits for pill-counts and phone contact at least once between these visits. In addition to these visits, the participants in the treatment group will be contacted by telephone at least monthly to inquire about medication side effects and to review changes in diet and exercise. Due to our involvement in the TODAY study and other trials of metformin, our staff are experienced with working on long-term projects with obese and T2DM adolescents, with excellent study retention out as far as four years.

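### Two visit schedules conflict on visit numbering, final-visit procedures and, only for participants at Tanner V before month 24, the treatment-stop date

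*Combined protocol and SAP*

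**What the plan says.** **Specific Aims (section A).** Aim 1 plans "frequently sampled IVGTT in early puberty and at puberty completion in obese and normal weight adolescents". Aim 2 plans IVGTT in early puberty, "at the end of puberty when treatment is stopped, as well as six months after treatment completion", and adds that "changes in inflammatory markers will be measured in all participants at these time points".

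**Specific Aim 1, Approach (schedule A).** "The next study visit (Study Visit 2) will occur when the participant has reached Tanner stage IV", about a year after baseline. Then "Study Visit 3) will occur when the participant has reached Tanner stage V, approximately one year after Study Visit 2". "The obese subjects will stop taking the study medication at this time point". Finally, "The next study visit (Study Visit 4) will occur 6 months after the obese participants have reached Tanner stage V"; laboratory draw, imaging other than MRI, and IVGTT are repeated there. The text counts four DEXA scans per obese participant, and the treatment table marks IVGTT and DEXA at Visit 4. MRI is for a subset of 13 per group.

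**Specific Aim 2, Approach (schedule B).** Treatment lasts two years and continues to Tanner V if that stage has not been reached by then. The baseline visit is repeated twice: at the end of treatment (Visit 2) and six months after stopping (Visit 3), with DEXA, MRI and NMR also repeated. There is no Tanner IV visit. The next paragraph restricts Visit 3 to IVGTT and anthropometry. The laboratory list under Specific Methods nevertheless includes Visit 3 for obese participants.

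**Potential Difficulties and Limitations/Alternatives.** Visit 3 is delayed until Tanner V is attained. Later in the same paragraph, "the interval from treatment stop (Study Visit 2) to post-treatment follow-up (Study Visit 3), should be consistent".

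**Statistical analysis.** The main regressions use a two-year change in each outcome, with two-year change in percent body fat and in BMI among the suggested confounders. The analysis is repeated for the change from baseline to six months post-treatment. No visit number or Tanner stage is named.

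**The concern.** The same visit number denotes different measurements. Visit 2 is an on-treatment Tanner IV assessment in schedule A and the end-of-treatment assessment in schedule B. Visit 3 is treatment stop in one and post-treatment follow-up in the other. The limitations section itself says that Tanner IV insulin sensitivity may not differ from earlier puberty, so the two are not interchangeable as an endpoint.

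The disagreement about the final visit affects what data will exist. Site staff who follow the restricting sentence would draw no inflammatory markers after treatment, although Aim 2b promises them, and would do no final DEXA. Neither can be recovered later.

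For a participant who reaches Tanner V early, the length of exposure to study medication depends on which section is followed.

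**Working it through.** **1. The plan's own counts.** Schedule A states four DEXA scans and two MRIs per obese participant. DEXA at Visits 1, 2, 3 and 4 gives 4. MRI at Visits 1 and 3 gives 2. Both reproduce, so schedule A is consistent with itself on imaging.

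**2. Counts per obese randomised participant under each reading.** B1 takes the Aim 2 visit as fully repeated twice; B2 applies the restricting sentence at the last visit.

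| Procedure | A | B1 | B2 |
|---|---|---|---|
| IVGTT | 4 | 3 | 3 |
| DEXA | 4 | 3 | 2 |
| Laboratory draws | 4 | 3 | 2 |
| MRI (subset of 13 per group only) | 2 | 3 | 2 |

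The Specific Methods list supports B1 for laboratory draws and contradicts B2. For MRI at the last visit, the conflict lies within Specific Aim 2 alone, because schedule A omits it too. Normal-weight participants have 3 laboratory draws under schedule A (Visits 1–3) and 2 under the Specific Methods list (Visits 1 and 2).

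**3. Treatment stop.** Let t be the month in which Tanner V is recorded.

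- Schedule A: stop = t, last IVGTT = t + 6.
- Schedule B: stop = max(24, t), last IVGTT = max(24, t) + 6.
- Difference in exposure = max(24, t) − t, which is 24 − t when t < 24 and 0 otherwise.

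| t (assumed) | Stop A | Stop B | Difference | Last IVGTT A | Last IVGTT B |
|---|---|---|---|---|---|
| 12 | 12 | 24 | 12 | 18 | 30 |
| 15 | 15 | 24 | 9 | 21 | 30 |
| 18 | 18 | 24 | 6 | 24 | 30 |
| 21 | 21 | 24 | 3 | 27 | 30 |
| 24 | 24 | 24 | 0 | 30 | 30 |
| 30 | 30 | 30 | 0 | 36 | 36 |

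The t values assume the quarterly staging of Specific Aim 2; under the six-monthly staging in the Specific Aim 1 text only 12, 18, 24 and 30 apply. On the plan's expectations (about one year to Visit 2 and one more to Visit 3), t = 12 + 12 = 24 and the schedules agree. Time off drug before the last IVGTT is (t + 6) − t = 6 months under A and (max(24, t) + 6) − max(24, t) = 6 months under B.

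**4. Persistence model.** The outcome runs from baseline to six months after stopping. Under B2 the last DEXA is at treatment stop, so a percent-body-fat change would end six months before the outcome does. BMI change remains available, because anthropometry is kept. Under A or B1 the problem does not arise.

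**5. The two-year label.** If t = 18, a literal month-24 value is 24 − 18 = 6 months off drug under A and the end-of-treatment value under B. If t = 30, the change to the end of treatment spans 30 months under both.

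**6. Power.** The stated 93% is a three-group ANOVA with changes 1.16, −0.17 and 1.6, SD 1.85 and n = 30. The grand mean is 2.59/3 = 0.863 and the sum of squared deviations about 1.70, so λ = 30 × 1.70/1.85² ≈ 14.9. With 2 and 87 degrees of freedom, power is 0.9345, which reproduces the figure. None of these inputs depends on visit numbering.

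**The case against.** Schedule A contains every IVGTT time point in the aims and in schedule B (baseline, treatment stop, six months later) and adds Tanner IV. A summary of aims may omit an interim visit without contradiction, and the visit table gives procedures visit by visit. On this view the plan has a numbering clash and one stray sentence. Much of that is fair: the silence of the aims on Tanner IV is not a conflict. But nothing gives the table precedence, and Specific Aim 2 is the approach section for the randomised comparison.

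Four stronger readings are tempting, and the documents do not support them:

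- **That the limitations paragraph certainly uses both numberings.** Its sentence delaying Visit 3 until Tanner V fits schedule A better, but it does not say that Visit 3 ends treatment. The preceding sentence concerns post-treatment measurement, so a schedule B reading is possible.
- **That participants would have different off-drug times at the last IVGTT.** Each schedule gives six months. A shorter interval needs the stop from B and the final visit from A (at t = 18, stop at 24 and visit at 18 + 6 = 24), which no section prescribes.
- **That the main endpoint is undefined.** The aims and the limitations section point to the end of puberty.
- **That the persistence model could not be fitted.** The confounder list is illustrative and BMI change survives; what is lost is a percent-body-fat change over the matching interval.

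**Conclusion.** The conflict is real and should be fixed, but it does not threaten the design. Numbering and final-visit content conflict for every obese randomised participant: DEXA 4, 3 or 2 and laboratory draws 4, 3 or 2, depending on the reading. The most consequential item is the sentence restricting the last visit, which contradicts the aims, schedule A and the protocol's own laboratory list.

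The treatment-stop conflict is confined to participants at Tanner V before month 24. Its size is 24 − t months for assumed t. A 12-month difference would need Tanner V at the time the plan expects Tanner IV. The number affected is not given. Specific Aim 2 expects most participants to be at Tanner V by two years, so the group cannot be assumed empty, but nothing shows that it is large. Which stopping statement should govern is not judged here.

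The two-year label is a minor gap that the aims largely close.

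**What to change.** - Reconcile the Specific Aims, both Approach sections, Specific Methods and the limitations section into one visit map per group, with one numbering and one list of IVGTT, laboratory, DEXA and MRI procedures per visit.
- Remove or reconcile the sentence restricting the last visit, so that laboratory draws and DEXA there agree with Aim 2 and schedule A. Otherwise, state that the persistence model omits percent body fat and that Aim 2b has no post-treatment markers.
- Reconcile the treatment-stop statements for participants reaching Tanner V before two years, and the anchor of the final visit (Tanner V or treatment stop). The sponsor decides which applies.
- In Statistical analysis, replace the two-year label, for outcomes and covariates, with change from baseline to the end-of-puberty (Tanner V) IVGTT visit. Identify it by its reconciled visit number: the visit six months later is also at Tanner V, so the stage alone does not single it out. Report actual intervals by group.

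The cost is a wording amendment; every procedure is already written into one of the two schedules. The downside is that intervals will vary between participants and must be reported. No stated sample size or power changes.
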